17.3. Semi-structured Interview Guides

Protocol and Interview Guide

Patient and Parent

Baseline

Version 1.0

1. Context and objectives

Advicenne is currently developing ADV7103, an innovative formulation of potassium citrate in the form of micro-tablets for the treatment of distal renal tubular acidosis.

Distal renal tubular acidosis (dRTA) is a condition characterised by a renal defect in hydrogen ion secretion in the distal renal tubules, inducing a hyperchloremic metabolic acidosis (low blood pH = less than 7.35) with no urine acidification.

Usually in non-dRTA subjects, the blood pH is about 7.4 corresponding to a blood concentration of bicarbonate of 21 to 28 mmol/L. A metabolic acidosis corresponds to a blood pH below 7.35 with a bicarbonate blood concentration lower than 22 mmol/L (or 22 mEq/L) (Chan, Scheinman et al. 2001).

Major biological signs of dRTA are usually a hyperchloremic metabolic acidosis, hypokalaemia and hypercalciuria, with a high pH of urine (>6.5), inducing nephrocalcinosis or lithiasis without treatment. In most cases, the condition causes osteomalacia in adults and short stature to rickets in infantile forms. In some genetic forms, deafness could be linked to mutation.

Distal renal tubular acidosis could be an inherited condition induced by genetic mutations or a secondary condition related mainly to autoimmune diseases (e.g. primary Sjögren's syndrome, systemic lupus erythematosus, primary biliary cirrhosis, autoimmune hepatitis).

There is no curative treatment of dRTA. This blood pH dependence of symptoms is the basis of the medical treatment of dRTA, which relies on alkalisatation to maintain a blood pH of 7.4 with a bicarbonate blood concentration above 22 mmol/L (Chan, Scheinman et al. 2001).

Alkali therapy, as sodium bicarbonate and potassium bicarbonate or tripotassium citrate, is used in dRTA to stabilise correction of metabolic acidosis and improves clinical spectrum of patient inducing a minimisation of stone risk and a better growth if treatment is early instituted. No effect was noticed on deafness. The aim of alkali therapy is to achieve a normal blood bicarbonate concentration (22 to 24 mEq/L). A continuous treatment is necessary to observe clinical improvement, using a mean alkali therapy of 1-2 mEq/kg/day in adults and of 4-8 mEq/kg/day in children where bicarbonate losses are frequently higher than in adults (Chan, Scheinman et al. 2001; Rodriguez Soriano 2002).

Currently available potassium citrate formulations exhibit low adherence characteristics, particularly in the pediatric population. In fact, the doses must be administered up to every 6 hours in 24 hours, including an administration during the night. In addition the formulations involve gastro-intestinal side effects and have a bitter taste.

Comparatively, ADV7103 has three advantages. It: (1) is tasteless and easy administration, particularly in young children, (2) reduces gastrointestinal side effects with intestine, and (3) requires only two doses per 24 hours.

The ARENA clinical development program of ADV7103 for dRTA consists of

- ARENA 1 is a cross-over study comparing dRTA standard of care to ADV7103 and the associated long-term extension study. ADV7103 proved to be non-inferior to SoC in maintaining serum bicarbonate levels above the lower limit of normal, and in fact, demonstrated superiority on this parameter. ADV7103 also maintained serum potassium levels in a safe range and showed good tolerability compared to SoC.
- ARENA 2 is a randomized withdrawal study comparing the ability of ADV7103 to prevent the development of metabolic acidosis compared to placebo, over 6 days. B24CS is the associated long-term open label roll-over study.

As part of the B23CS (ARENA 2) study, Advicenne commissioned MAPI/ICON to conduct qualitative research based on semi-structured interviews at the beginning of the study ("baseline") and then at the conclusion of the stabilization period, approximately 8 weeks later. Over the course of the two interviews, the intent is to explore the patient's perspective on:

- dRTA and treatments that patients currently use to manage dRTA (standard of care/SOC) and the impact of dRTA and current treatment options on patients' daily lives;
- patients' attitudes, beliefs and behaviors related to dRTA and its treatment;
- how dRTA itself and how they have treated their dRTA have evolved over time;
- what changes, if any, they have experienced while taking ADV7103;
- whether the experience of taking ADV7103 is the same, better, or worse than taking the SOC;
- whether they would want to continue to use it, if ADV7103 is approved and becomes available, and why/why/not;
- whether having ADV available might cause them to make any changes in how they treat their dRTA.

This guide presents the instructions and the method to be used to conduct interviews at the beginning of the study ().

2. Methods

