- Second Study Period (SP II) of 3 to 30 days: switch from SOC to ADV7103 twice a day for a titration phase up to the optimal dose;
- Third Study Period (SP III) of 5 days: maintenance of treatment with ADV7103 twice a day at the fixed optimal dose.

The primary objective of Study B21CS was to evaluate the relative efficacy of ADV7103 and SOC on correcting metabolic acidosis as measured on pre-morning dose blood bicarbonate levels after 4 days of treatment at steady state (comparison of residual blood concentration of bicarbonate on SPIII Day 2 t0, Day 3 t0, Day 4 t0 to residual blood concentration of bicarbonate on SPI Day 2 t0, Day 3 t0, Day 4 t0).

Preliminary data revealed that blood bicarbonate levels were lower after SOC than after ADV7103 administration. Using a target therapeutic level of blood bicarbonate concentration of 22 mmol/L, SOC therapy provided suboptimal correction of acidosis for the pediatric subjects, with high variability observed in the adult subjects. When switched to ADV7103 twice daily, the blood bicarbonate concentrations increased overall indicating good control of the metabolic acidosis, with twice daily administration of ADV7103 at least as effective as SOC therapy.

The doses of ADV7103 taken in this study ranged from 0.75 mEq/kg/day to 8.45 mEq/kg/day, for periods from 15 to 43 days. The maximal dose provided was for a child who needed 6 mEq/kg/day, or 334 mEq/day. The doses of alkalizing agents used across the age groups of subjects indicated that, while the total daily dose of alkalizing agent was similar with SOC and ADV7103 for adults and adolescents, it increased in younger children and infants. However, the

doses of ADV7103 are in accordance with the doses of alkalinating agents reported in the literature regardless of age.

These preliminary data, in combination with clinical experience, indicate that the alkali dose was not optimized with the SOC treatment, particularly in these younger age groups. From the investigator's point of view, the SOC dosing may be limited by gastrointestinal issues, whereas ADV7103, better tolerated by subjects, may facilitate more appropriate dosing. Additionally, SOC typically requires administration several times a day, which leads to adherence issues; alternatively, twice daily administration of ADV7103 (morning and evening), may promote better adherence.

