5.3. Exploratory Objectives

- Compare the gastrointestinal tolerability, measured on an age appropriate scale, of ADV7103 (Visit 2) versus SOC (Visit 1);
- Compare urinary supersaturated (SS) calcium oxalate, SS calcium phosphate, and SS uric acid levels: ADV7103 (Visit 2) versus SOC (Visit 1) and ADV7103 vs. placebo (Period 3);
- Compare age appropriate study product acceptability and satisfaction scores: ADV7103 (Visit 2) versus SOC (Visit 1);
- Compare palatability and ease of administration/swallowing and number of daily product intakes scores: ADV7103 (Visit 2) versus SOC (Visit 1);
- Evaluate quality of life variables through use of questionnaires and semi-structured interviews.

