Alkali therapy, as sodium bicarbonate and potassium bicarbonate or tripotassium citrate, is used in dRTA to stabilise correction of metabolic acidosis and improves clinical spectrum of patient inducing a minimisation of stone risk and a better growth if treatment is early instituted. No effect was noticed on deafness. The aim of alkali therapy is to achieve a normal blood bicarbonate concentration (22 to 24 mEq/L). A continuous treatment is necessary to observe clinical improvement, using a mean alkali therapy of 1-2 mEq/kg/day in adults and of 4-8 mEq/kg/day in children where bicarbonate losses are frequently higher than in adults (Chan, Scheinman et al. 2001; Rodriguez Soriano 2002).

Currently available potassium citrate formulations exhibit low adherence characteristics, particularly in the pediatric population. In fact, the doses must be administered up to every 6 hours in 24 hours, including an administration during the night. In addition, the formulations involve any side effects are gastro-intestinal to and have a bitter taste.

Comparatively, ADV7103 has three advantages, it: (1) is tasteless and easy administration, particularly in young children, (2) reduces gastrointestinal side effects with intestine, and (3) requires only two doses per 24 hours.

The ARENA clinical development program of ADV7103 for dRTA consists of

- B21CS (ARENA 1) and B22CS: ARENA 1 is a cross-over study comparing dRTA standard of care to ADV7103 and the associated long-term extension study. ADV7103 proved to be non-inferior to SoC in maintaining serum bicarbonate levels above the lower limit of normal, and in fact,

demonstrated superiority on this parameter. ADV7103 also maintained serum potassium levels in a safe range and showed good tolerability compared to SoC.

- B23CS (ARENA 2) and B24CS: ARENA 2 is a randomized withdrawal study comparing the ability of ADV7103 to prevent the development of metabolic acidosis compared to placebo, over 6 days. B24CS is the associated long-term open label roll-over study.

As part of the B23CS (ARENA 2) study, Advicenne commissioned MAPI/ICON to conduct qualitative research based on semi-structured interviews at the beginning of the study (" baseline "), and then at the conclusion of the stabilization period, approximately 8 weeks later. Over the course of the two interview, the intent is to explore the patient's perspective on :

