- dRTA and treatments that patients currently use to manage dRTA (standard of care/SOC) and the impact of dRTA and current treatment options on patients' daily lives;
- patients' attitudes, beliefs and behaviors related to dRTA and its treatment;
- how dRTA itself and how they have treated their dRTA have evolved over time.

This guide presents the instructions and the method to be used to conduct interviews at the end of Stabilization ("Period 2").

2. Methods

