Theme 2: Experiences with taking ADV7103

Is there anything in particular that you remember about the new study medication when you first started taking it during the clinical study?

Preparation (set-up) – What do you have to do, if anything, to prepare to take the study medication before you take it? Is this different than how it was with the medication you took before you started the clinical study? How so?

Please list all the things that are the same and all the things that are different about the new study medication as compared to the medication you took before the clinical study? If not mentioned, probe taste, texture, doses in 24 hrs, how you feel after you take it.

Adherence / monitoring of the prescription – how easy or difficult do you think it will be for you to follow the directions and take the medication as directed when you are no longer in the clinical study? Why?

Reasons / motivations to follow (or not) the prescription – During the baseline interview, if the patient mentioned reasons why he/she took the medication less often than he/she was supposed to take it, ask whether those same reasons would apply to the study medication.

Theme 3: Overall satisfaction, expectations for treatment, and meaningful improvements

Satisfaction

Using a scale from 1-10 with 1 = not satisfied at all and 10 = completely satisfied, how satisfied would you say you are overall with the study medication?

Factors / reasons for satisfaction (or dissatisfaction)- list all

Expectations

Overall, would you say the study medication has:

- Not met my expectations/is not as good as I thought it would be
- Has met my expectations/ about the same as I thought it would be
- Has exceeded my expectations/ is better than I thought it would be

Why did you say the study medication (did not meet, met, or exceeded) your expectations?

Meaningful Improvements

What, if any improvements, have you experienced on the study medication that are meaningful to you?

5. End of the interview

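### Both interview guides brief interviewers with favourable claims about ADV7103 stated as fact, and the only item on meaningful change asks about improvement without a counterpart on worsening

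*Combined protocol and SAP*

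**What the plan says.** Section 10.2.16 plans an interview near Visit 1 and another at the end of the Stabilization Phase. The second is meant to compare experience on SOC with experience on ADV7103. The results are an exploratory endpoint (Section 6.3.3).

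Section 17.3 contains the two guides. Each begins with a context section for the interviewer:

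- Existing potassium citrate products are described as poorly adhered to, bitter and hard on the gut.
- The baseline guide then states: "Comparatively, ADV7103 has three advantages. It: (1) is tasteless and easy administration, particularly in young children, (2) reduces gastrointestinal side effects with intestine". The third advantage listed is twice-daily dosing. The post-stabilization guide repeats the passage: "Comparatively, ADV7103 has three advantages, it: (1) is tasteless and easy administration".
- Both guides report that in the earlier crossover study ADV7103 was non-inferior to SOC in maintaining serum bicarbonate, "and in fact, demonstrated superiority on this parameter".

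The baseline guide lists as an aim "whether the experience of taking ADV7103 is the same, better, or worse than taking the SOC". The post-stabilization guide has a shorter list of aims, which ends at "how dRTA itself and how they have treated their dRTA have evolved over time".

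The last content item of the post-stabilization guide is "What, if any improvements, have you experienced on the study medication that are meaningful to you".

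Section 5.3 makes several of the briefed attributes objectives of this trial, for example: "Compare the gastrointestinal tolerability, measured on an age appropriate scale, of ADV7103 (Visit 2) versus SOC (Visit 1".

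**The concern.** Interviewers are given as fact some of what the study sets out to learn. Participants know they have moved from their own treatment to ADV7103, so there is no blinding to offset an interviewer's expectation. The interviewer presents the study, answers questions before starting, and chooses which probes to use and how far to pursue them.

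The interviews are also meant to show whether subjects find ADV7103's benefits meaningful. If meaningful improvement is asked for directly and meaningful worsening is not, a report can cite the first without any directly elicited evidence on the second. At stake is the credibility of the qualitative evidence on patient experience.

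**Working it through.** The plan gives no figure on this point and no formula applies. The check sets the briefing, the aims and the scripted items side by side.

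**1. Briefing against study questions.** Section 10.2.15.5 names five acceptability attributes: palatability, ease of administration, ease of swallowing, number of daily intakes and gastrointestinal tolerability. The briefing gives a favourable answer on three of the five: taste, ease of administration and gastrointestinal effects. It also mentions the number of intakes, but twice-daily dosing is simply the regimen; what the study rates is how convenient subjects find it. I therefore count three attributes, not four. Section 4.3.2 is more careful than the guides: it lists better gastrointestinal tolerability and less reluctance to take the product among anticipated benefits.

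**2. Other statements in the briefing.** Section 4.1.4 describes the earlier study's data as preliminary and concludes "twice daily administration of ADV7103 at least as effective as SOC therapy"; the guides speak of superiority on bicarbonate. The guides also call the product a potassium citrate micro-tablet, whereas Section 9.1.1 describes prolonged-release granules of potassium citrate and potassium bicarbonate. The second mismatch is an inaccuracy to correct, not evidence of a tilt.

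**3. Scripted items in the post-stabilization guide.**

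| Item | Direction |
|---|---|
| What, if anything, has changed | neutral |
| Probe on symptoms and impacts raised at baseline | neutral |
| What is remembered from first taking the product | neutral |
| Preparation, and whether it differs from before | neutral |
| List of what is the same and what is different | two-sided |
| How easy or difficult following directions will be | two-sided |
| Whether earlier reasons for missing doses would still apply | two-sided |
| Satisfaction from 1 to 10 | two-sided |
| Reasons for satisfaction or dissatisfaction | two-sided |
| Expectations not met, met or exceeded, and why | two-sided |
| Meaningful improvements | improvement only |

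That is 10 + 1 = 11 items; splitting sub-questions differently changes the total slightly. Items on meaningful improvement: 1. Items on meaningful worsening: 0. This follows the topic list in Section 10.2.16, which names meaningful benefits and no matching topic on drawbacks.

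**4. The three-way comparison.** The same-better-worse aim stands in the baseline guide, used before the subject has taken ADV7103. It is missing from the aims of the guide used afterwards, and 0 scripted items in either guide put it to the participant. The nearest item asks what is the same and what is different, without asking in which direction.

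**5. Baseline side.** The baseline guide asks how close the current treatment comes to an ideal product and where it falls short. No later item puts ADV7103 against the same ideal; the expectations item is only a partial match.

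**6. Routes from briefing to data.** Nothing tells the interviewer to read the advantages aloud. Remaining routes are the presentation of the study, answers to participants' questions, choice of probes from a list described as not exhaustive, and notes from memory if recording fails. The post-stabilization guide also prompts on taste, texture, daily doses and how the person feels after a dose when these are not raised, which overlaps with the briefed advantages.

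**The case against.** The strongest reply is that the guide is largely balanced and the briefing is only background. Much of this stands:

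- The introduction given to participants is neutral, and they are told to answer honestly.
- Unprompted answers come before probes. Interviews are recorded with permission and run by trained, experienced external interviewers (Section 10.2.16).
- The five attributes are rated on separate hedonic and visual analogue forms by the subject or parent, and preference has its own three-option item that includes the previous treatment. None of these is scored from the interview.
- Participants' own knowledge of the switch is a source of bias that no rewording removes.

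A reader might infer more than the text supports. One reading is that the post-stabilization guide asks only about improvements; the table above contradicts it, since dissatisfaction, difficulty and unmet expectations are all asked about. Another is that interviewers are told the product is superior and then ask whether it is the same, better or worse. The superiority statement is confined to serum bicarbonate, and the three-way comparison is an aim, not a scripted question. Nor is the wording in Section 4.1.4 a proven contradiction: it describes preliminary data, reports lower bicarbonate on SOC, and may predate the statement in the guides.

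What the reply does not meet is narrower. The favourable claims are unnecessary for conducting the interview. General probes on dissatisfaction do not ask whether anything became worse in a way that matters. And the comparative aim is lost from the guide used after exposure.

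**Conclusion.** The point holds as a cheap improvement. Both guides (2 of 2) brief interviewers with favourable statements on three attributes under comparison and on bicarbonate. One of about 11 post-stabilization items is one-sided, and it is the only one on meaningful change. The three-way comparison with SOC is scripted nowhere.

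This is a risk of tilt, not a demonstrated one, and the documents give no basis for putting a size on it. The judgement assumes that interviewers read the context section and that expectation can influence probing and note-taking even when the opening script is neutral. It would be tempting to call the interview results biased by design; the neutral introduction and mostly two-sided items do not support that. The consequence is confined to an exploratory qualitative endpoint, collected before Period 3 or at early withdrawal. The primary endpoint, its power and the separate rating-scale scores are not affected.

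**What to change.** In Section 17.3:

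1. In both guides, replace the advantages and superiority text with a neutral product description consistent with Section 9.1.1. This also removes the micro-tablet error.
2. In the post-stabilization guide, restore the comparative aim and script it: *Overall, is taking the study medication the same as, better than or worse than taking your previous treatment, and why?*
3. Directly after the meaningful-improvements item, add its mirror: *What, if anything, has become worse on the study medication in a way that is meaningful to you?*

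The cost is a text edit to the appendix and one or two extra questions within the existing interview of about 60 minutes, with no added visits or staff. If some interviews have already been held, record the guide version with each transcript so that the two sets can be read separately.

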2.1. The Interviewer

The roles and responsibilities of the interviewer are detailed below.

Before and at the beginning of the interview :

- Schedule an appointment with the patient (and / or their parent) for an interview;
- Offer the patient (and / or his or her parent) to use a video platform to perform the interview (Skype, WebEx ...) ;
- Ensure that the interviewer and the patient (and / or their parent) are in quiet locations, respectively, where the conditions guarantee the free expression of the patient (and / or their relative) and confidentiality, without interruption;
- Ensure the proper operation of the recording device/system; if the recording equipment uses batteries, use new batteries at each interview;
- Receive training and know the procedure to follow in case of spontaneous notification of adverse effects;
- Check that the patient (and / or their parent) has been informed (s) and has / have agreed to participate in the interview;
- Recall the purpose of the interview to the patient (and / or parent), and what is expected of him / her / them;
- Remind the patient (and / or their parent) of the confidentiality and anonymity of the information they / he / she will report; his / their answers will be forwarded only to those involved in the study and will not be linked to his / her name (s);
- Remind the patient (and / or their parent) that the interview is being recorded and ask for verbal consent before starting the interview and while recording;
-
- Answer any questions that the patient (and / or their parent) may have before starting the interview

After the interview :

- Check the recording; in case the interview has not been recorded, take detailed notes based on recent memory (if convenient and not distracting, notes should also be taken during the interview);
- Rename the audio: 060482 _ [patient ID] _ [patient +/- parent] _ baseline_Date [DD-MMM-YYYY]. Download the audio file to the secure server. If notes have been taken, the annotated document must be scanned, renamed as before and uploaded to the secure server along with the audio file ;
- Classify the adverse reaction reporting report in the event that the patient (and / or their parent) has spontaneously reported an adverse reaction to a sponsor product during the course of the interview. The investigator must report an adverse event according to the procedure described in section 2.3 of this document.

